9.7.2 Pooled Analysis

The coordinating center will conduct an analysis of the propensity score-stratified data from each individual database and an overall analysis combining the data across all database research partners. For the JOELLE Extension, because data from Denmark cannot be shared outside the country, data from each data source will be centralized on the servers of Statistics Denmark through the University of Southern Denmark, and the coordinating center will conduct the pooled analysis remotely within these servers. The overall analysis will be designed to estimate the effect of the exposure while controlling for confounding using the data stratified on propensity scores. Mantel-Haenszel methods will be used to summarize effects across strata. Data source will be retained as a stratification variable, and the effect within each data source will be estimated. If some strata have zero cases, it may be possible to collapse neighboring propensity score strata within sites without introducing confounding, yielding fewer than 10 strata per site in the final stratified analysis. Before the final analysis, the amount of confounding reintroduced by collapsing of neighboring strata will be evaluated.

9.7.2.1 Stratification by Type of Prescriber (Dermatologist vs. Other Prescribers)

Data from prior studies and from Phase I of the JOELLE study have shown that type of prescriber of the first prescription (e.g., dermatologist versus nondermatologist) can be a confounder of the association between study medications and skin cancer [23]. In Phase I, information on type of prescriber was available in PHARMO and Sweden but not in Denmark or the CPRD. We evaluated the confounding effect of type of prescriber through a quantitative bias analysis for unmeasured confounders to account for the lack of information in Denmark and CPRD. In the JOELLE Extension, information on type of prescriber is also available in Denmark. To evaluate the potential bias for the uncontrolled effect of type of prescriber in the CPRD, an additional analysis restricted to users in PHARMO, Denmark, and Sweden will be conducted in the JOELLE Extension. Based on the number of users included in Phase I, this additional analysis is estimated to include approximately 90% of children and 79% of adults from the whole study cohort (including the CPRD).

9.7.2.2 Estimation of Incidence Rates

Incidence rates will be estimated separately for children and adults. Crude incidence rates will be calculated for each data source and overall across all data sources as the number of outcome events divided by the person-time at risk. The Poisson distribution will be used to calculate exact 95% CIs for the incidence rates within each data source. Standardized incidence rates will be estimated using the distribution of person-time across deciles of propensity scores of the cohort exposed to tacrolimus as the standard. Crude and standardized incidence rates for each study endpoint will be estimated for each exposure category of each study cohort: tacrolimus cohort, pimecrolimus cohort, and the two corticosteroids cohorts. Crude and standardized incidence rates for exposure to tacrolimus and pimecrolimus will be estimated initially for ever use, single use, and switching/multiple use. The main exposure of interest will be cumulative dose, which will be estimated for each exposure category (ever use, single use, and switcher/multiple use). Crude and standardized incidence rates will be also estimated by duration of exposure.

9.7.2.3 Estimation of Incidence Rate Ratios

The coordinating center will use Mantel-Haenszel methods for the pooled analysis. Incidence rate ratios and 95% CIs will be estimated, stratifying by deciles of propensity scores, age categories, sex, and database research partner. To control for confounding, the Mantel-Haenszel analysis will provide pooled estimators that summarize the effect of exposure across strata of propensity scores and database partner. Incidence rate ratios will be estimated separately for children and adults. Crude and adjusted incidence rate ratios and 95% CIs for each study endpoint will be estimated, comparing the incidence rates for each exposure category (ever use, single use, and switcher/multiple use) of topical tacrolimus and topical pimecrolimus with the rates in the corresponding corticosteroids cohort. The analysis will focus on the estimation of incidence rate ratios comparing the incidence rates for each category of cumulative dose and duration of exposure to tacrolimus and pimecrolimus (e.g., low, medium, high) with the rates in the corresponding corticosteroids cohort. These rate ratios will be estimated separately for the periods of ever use, single use, switching/multiple use, and combined multiple use.

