Data analysis: The study cohorts will be followed from the start date for the first occurrence of any one of the study endpoints. A minimum lag time of 6 months will be assumed between the start of exposure and the occurrence of related study endpoints. Person-years of follow-up will be classified according to ever use, single use, and switching/multiple use of tacrolimus and pimecrolimus and to cumulative dose and duration of exposure. The main exposures of interest will be the cumulative dose of topical tacrolimus and pimecrolimus and time since first exposure.

The analysis will be conducted at two levels: a country-specific analysis conducted at each database research partner and an overall analysis conducted at the coordinating center. The approach is for each database research partner to create stratified tables with cross-classifications of patient and person-time counts by exposure category, endpoint, deciles of exposure propensity scores, age, sex, data source, and type of prescriber of first prescription when available. The coordinating center will estimate overall measures of effect through a stratified analysis of the data from the database research partners. Mantel-Haenszel methods will be used to summarize effects across strata. Crude and adjusted incidence rate ratios for each study endpoint and exposure category will be estimated comparing users of tacrolimus and users of pimecrolimus with users of corticosteroids. A secondary analysis will compare users of corticosteroids with untreated patients. Sensitivity analyses will be conducted to evaluate protopathic and surveillance bias. Separate analyses will be conducted for the pediatric and adult populations.

Milestones:

The study protocol version 4.0 dated April 10, 2013, was approved by the EMA.

The study was registered in the EU PAS Register in July 30, 2013 (<http://www.encepp.eu/encepp/viewResource.htm?id=4358>).

Phase I of the study was completed November 30, 2015. The study report was submitted to the EMA on December 11, 2015.

The JOELLE Extension involves the inclusion of 4 years of additional data. Depending on data availability, the extension may be longer in some of the study databases. The start of data collection is planned between Q3 2017 and Q1 2018. The final study report is expected to be completed in Q3 2019.

5 Amendments and Updates

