When estimating incidence rates we will assume a minimum lag time of 6 months between the start of treatment and the occurrence of the study endpoints. This implies that person-time for the interval of the first 6 months since start of treatment will be excluded, along with any events that occur within this time period. This lag time encompasses a period of drug utilization and dose accumulation, a period of induction time (from causal action of exposure to disease initiation), and a latency period (from disease initiation to disease detection). The induction time for the occurrence of skin cancer and lymphomas associated with the use of tacrolimus and pimecrolimus is unknown. Therefore, we will conduct sensitivity analyses to estimate incidence rates within the first 6 months of treatment and for several lag times longer than the initial 6 months. The lag time analysis will also be used to explore potential protopathic bias if early symptoms of skin cancer or lymphoma are erroneously treated as atopic dermatitis and therefore the reason for starting treatment.

The goal of the first secondary objective is to obtain background rates among persons not treated with the study medications and to put in perspective potential differences among the untreated population, the atopic dermatitis cohort treated with moderate- to high-potency corticosteroids (see Section 9.3.1, Identification of Atopic Dermatitis, for further details on atopic dermatitis criteria), and the tacrolimus cohort.

9 Research Methods

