9.3.4.4 Cumulative Exposure

Cumulative exposure will be used as the main measure of exposure in the analysis and will be calculated as the cumulative dose of tacrolimus or pimecrolimus a patient receives during follow-up. Dose will be accumulated daily according to the milligrams prescribed and the estimated average duration of prescriptions. The milligrams prescribed will be calculated according to the strength of the formulation and the package size. The average duration of prescriptions will be estimated separately for children and adults from preliminary descriptive analysis of the time between consecutive prescriptions. The average duration of prescriptions used in Phase I will be used in the JOELLE Extension.

Cumulative exposure will be categorized in levels of exposure (e.g., low, medium, and high) according to the distribution of cumulative exposure in the study databases. The number of levels of cumulative exposure and cut-off values will be decided after examining the distribution of cumulative exposure across databases. Patients will contribute time of follow-up to each level of cumulative exposure according to the cumulative dose received. For each level of cumulative exposure, we will assume an induction period of 6 months for the start of exposure effects. Thus, the time at risk will start 6 months after reaching the cut-off value of each cumulative exposure category. Cumulative exposure will be assessed for tacrolimus and for pimecrolimus for each of the exposure categories described in Section 9.3.4.1 (ever use, single use, and switching/multiple use) and for combined multiple use of both tacrolimus and pimecrolimus (Section 9.3.4.3).

[figure not shown]

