9.3.4.6 Cohort of Users of Corticosteroids

Person-time will be accumulated from the date of cohort entry to the earliest of the following dates: prescription for topical tacrolimus, prescription for topical pimecrolimus, or end of follow-up (Figure 5).

[figure not shown]
Figure 5. Exposure Assessment: Example for Patients Contributing Person-time to Both the Corticosteroids Cohort and the Tacrolimus Cohort

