9.7.1.4 Estimation of Propensity Scores

Estimation of propensity scores will be conducted separately for children and adults. For each age group, each database research partner will estimate two separate sets of propensity scores, one set for the analyses comparing users of tacrolimus with users of corticosteroids and another set for the analyses comparing users of pimecrolimus with users of corticosteroids.

The propensity scores, which are based on the values of the covariates at treatment initiation, will estimate the probability that each patient is prescribed the study drug (tacrolimus or pimecrolimus) rather than moderate- to high-potency topical corticosteroids. The propensity score will serve as a within-database variable that summarizes the confounding from a large set of variables. Propensity scores will be estimated using multiple logistic regression models. Covariates to be used for the estimation of propensity scores are those related to the probability of receiving treatment with tacrolimus or pimecrolimus and those associated with the risk of skin cancer and lymphoma. Covariates are measured before initiating treatment with the study medications. A list of covariates to be evaluated is presented in Annex 5. Selection of variables will be conducted using a high-dimensional propensity score algorithm [21]. This algorithm has been shown to perform well in the Danish databases [22]. Patients who contribute follow-up time to both the corticosteroids cohort and one of the exposed cohorts (tacrolimus or pimecrolimus) will be included twice in the model used to estimate propensity scores—once in the corticosteroids cohort, using covariate data values at the time of initiating corticosteroids, and once in the tacrolimus or pimecrolimus cohorts, using covariate data values at the time of initiating tacrolimus or pimecrolimus.

From the fitted propensity score model, a propensity score will be estimated for each patient (twice for any patient who contributes follow-up time to both a study drug cohort and the corticosteroids cohort). The database research partners will categorize exposure

propensity scores in 20 strata (twentiles). Trimming (excluding) nonoverlapping regions of propensity scores will be performed prior to any propensity score implementation.

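### Cumulative-dose, duration and switching categories accrue late in follow-up but are compared with unsplit corticosteroid person-time; time since start is not a stratum and the basis of age is undefined

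*Protocol*

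**What the plan says.** **Exposure.** Section 9.3.4.4: "Cumulative exposure will be used as the main measure of exposure in the analysis". The levels are time-varying: "Patients will contribute time of follow-up to each level of cumulative exposure according to the cumulative dose received", and "the time at risk will start 6 months after reaching the cut-off value of each cumulative exposure category". Under 9.3.4.1, switching/multiple use likewise begins 6 months after the second drug is prescribed.

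**Comparator.** Section 9.3.4.6, for the corticosteroid cohort: "Person-time will be accumulated from the date of cohort entry to the earliest of the following dates", those dates being a tacrolimus or pimecrolimus prescription or the end of follow-up. There is no split by time. Section 8 states a general lag ("person-time for the interval of the first 6 months since start of treatment will be excluded"), which 9.3.4.6 does not repeat.

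**Comparison.** Section 9.7.2.3 puts the focus on ratios of each dose and duration category against the corresponding corticosteroid cohort. Its strata: "Incidence rate ratios and 95% CIs will be estimated, stratifying by deciles of propensity scores, age categories, sex, and database research partner". The propensity scores are "based on the values of the covariates at treatment initiation" (9.7.1.4).

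**Age.** A later sentence of 9.7.2.3 describes the pooled, confounding-controlled estimator as running over propensity score strata and database partner only. Section 9.7 lists the site tables without age or sex, whereas the Abstract includes both.

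**Time since first exposure.** Abstract, Data analysis: "The main exposures of interest will be the cumulative dose of topical tacrolimus and pimecrolimus and time since first exposure". Sections 9.7.2.2 and 9.7.2.3 estimate nothing by it for tacrolimus or pimecrolimus. It returns under that name only in 9.7.2.6, for corticosteroids versus untreated patients.

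**The concern.** A patient must accumulate prescriptions to reach a higher dose level, or receive a second drug to count as a switcher, and then wait a further 6 months. Person-time in those categories therefore lies later after the start date than the average corticosteroid person-year. Within a stratum defined at baseline, later person-time belongs to older people. If incidence rises with age, the upper categories can show a ratio above 1 and a rising pattern across levels with no drug effect. That is the pattern this safety study is looking for, in the comparison it calls its focus.

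A propensity score fixed at initiation cannot correct a difference that develops during follow-up. Whether the age strata correct it depends on two things the protocol leaves unsettled: whether age is updated over follow-up, and whether it enters the adjusted estimator at all.

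**Working it through.** **Inputs**
- Adult follow-up distribution of tacrolimus users: Table 6 (103,175 users).
- Adult person-years after the 6-month lag: 551,369 (Table 3).
- Adult non-melanoma skin cancer (NMSC) rate: 286.2 per 100,000 person-years (Table 4).
- Assumptions not in the protocol: incidence rises by a proportion g = 3-7% per year of age; corticosteroid follow-up has the Table 6 shape; a category's time at risk starts at 3 or 5 years; age is taken at baseline.

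**Step 1: reproduce the plan's person-years.** The sum over Table 6 of users x band midpoint is 602,953.5. Subtracting the lag, 0.5 x 103,175 = 51,587.5, gives 551,366 against the stated 551,369. Table 6 is therefore a sound basis for the time axis.

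**Step 2: person-time after a delay.** Take the cumulative counts of Table 6 above the starting band, plus half the count at its start.
- After year 3: 274,317 + 82,403/2 = 315,518 person-years.
- After year 5: 143,078 + 59,856/2 = 173,006 person-years.

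**Step 3: mean time since start.** All person-time from entry: 3.63 years. After the 6-month lag: 3.95. After year 3: 5.64. After year 5: 7.03. Against a lagged comparator, late person-time is later by 5.64 - 3.95 = 1.69 years and 7.03 - 3.95 = 3.08 years.

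**Step 4: rate ratio with no drug effect.** Person-time-weighted mean of exp(g x t) in the late category, divided by the same mean over all comparator time, with a 6-month lag in both:

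| g per year | time at risk from year 3 | from year 5 |
|---|---|---|
| 3% | 1.05 | 1.10 |
| 5% | 1.09 | 1.16 |
| 7% | 1.12 | 1.23 |

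A rough check using mean times only: exp(0.03 x 1.69) = 1.05 and exp(0.07 x 3.08) = 1.24. If the comparator is counted from day 0, as 9.3.4.6 reads literally, the ranges become 1.06-1.14 and 1.11-1.25.

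**Step 5: against sampling error, adult NMSC.** Expected exposed events: 551,369 x 286.2/100,000 = 1,578. Share after year 3: 315,518/551,366 = 57%, about 903 events. Share after year 5: 173,006/551,366 = 31%, about 495 events. With 4:1 matching, take 4 x 1,578 = 6,312 comparator events (an upper bound, since the ratio is at most 4:1). The 95% interval factor is exp(1.96 x sqrt(1/E + 1/6,312)):

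| share of late person-time that is high dose (assumed) | from year 3: E, factor | from year 5: E, factor |
|---|---|---|
| all | 903, 1.07 | 495, 1.10 |
| one third | 301, 1.12 | 165, 1.17 |
| one fifth | 181, 1.16 | 99, 1.22 |

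Taking the shares on the unlagged 602,954 person-years instead (52% and 29%) widens each factor by no more than about 0.01.

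**Step 6: where the gradient sits.** In an illustrative simulation, 30-80% of users never left the low level, mean times to the medium and high levels were 2 and 4 years, and the comparator ran from day 0. For g = 3-8% the null ratios were about 0.94-1.01 (low), 1.03-1.08 (medium) and 1.08-1.23 (high). The distortion lies mainly in the upper levels.

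**The case against.** **Age is listed.** It is named in 9.7.2.3 separately from the propensity score, and the Abstract has person-time counts cross-classified by it. Because start-date age is already in the score, attained age is a natural reading of a separate stratum. Annex 5 lists score and descriptive variables and does not define the rate-ratio strata. This stands: a reader might infer that the plan ignores attained age, but the text supports only that the basis is undefined and its place in the adjusted estimator inconsistent. With attained age in the mostly 10-year adult bands of Annex 5, most of the age-driven part disappears.

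**The SAP may settle it.** Section 9.7 assigns variable creation, person-years and site input data to a separate plan, so the timing of age alone could be left there. But the protocol itself fixes a stratum list without time since start, contradicts itself on age, and names a main exposure that its analysis section drops.

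**Other lags are planned.** Section 9.7.2.5, item 7, covers the first 6 months and lags such as 12, 18, 24 and 48 months. These give some information by time from first exposure. Their stated purpose is protopathic bias, and they do not align dose levels with comparator time.

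**The delays are not documented.** Cut-offs await the observed distribution (9.3.4.4), so some users could reach a high level early. This stands; the 3- and 5-year figures are illustrations.

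**Sparse strata.** Eight adult age bands x three time bands x ten deciles x two sexes x four databases gives 1,920 cells per exposure category and endpoint. This is a real cost, though 9.7.2 already allows propensity score strata to be collapsed.

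**Conclusion.** The point holds as a modest risk of bias, not a demonstrated one. Time-varying dose, duration and switching categories are set against undivided corticosteroid person-time, time since start is not a stratum, and the role of age is unclear. If age is baseline age, the null rate ratio is about 1.05-1.12 for time at risk from year 3 and 1.10-1.23 from year 5, on the assumed age slopes, delays and equal follow-up in the two cohorts.

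A reader might go further and infer that a false dose-response is bound to appear and would look statistically clear. The documents do not support that. Clarity would require nearly all late person-time to be high dose (interval factor 1.07-1.10). At one third to one fifth, the factor of 1.12-1.22 is about as large as the bias. Adult NMSC is the endpoint where it matters most. In children, lymphoma has the highest rate in Table 4, and 133,285 x 2.1/100,000 gives only about 3 expected events, so random error dominates.

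The missing tacrolimus and pimecrolimus estimates by time since first exposure are a plain inconsistency between the Abstract and 9.7.2, and depend on none of these assumptions.

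**What to change.** In 9.7, 9.7.1.4 and 9.7.2.3:

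1. State that age is attained (time-updated) age, that site tables carry it, and that it enters the adjusted Mantel-Haenszel estimator. Bring the table descriptions in the Abstract and 9.7 into agreement.
2. Split person-time and events in the tacrolimus, pimecrolimus and corticosteroid cohorts by a few bands of time since start date (for example 0.5 to under 2, 2 to under 5, and 5 or more years), with the same 6-month lag in all. Say so in 9.3.4.6.
3. Use these bands as strata for the dose, duration and switching ratios, collapsing propensity score strata where sparse as 9.7.2 allows.
4. Report tacrolimus and pimecrolimus rate ratios by time since first exposure, as the Abstract states.

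The cost is larger site-level tables, sparser strata with some loss of precision for rare endpoints, and some small-cell disclosure handling. It should be settled before the sites build their tables: the coordinating center receives only stratified counts and cannot recreate the split afterwards.

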9.7.2.4 Estimation of Incidence Rate Differences

The main analysis is based on incidence rate ratios; however, additional analyses may be performed looking at incidence rate differences and numbers needed to harm.

9.7.2.5 Sensitivity Analysis

Sensitivity analyses will be conducted for single use of topical tacrolimus and topical pimecrolimus. The following sensitivity analyses will be conducted:

1. Incidence rates and incidence rate ratios will be estimated for the subgroup of children aged ≥ 2 to < 16 years, which is the age range for children specified in the labeling of topical tacrolimus.
2. Incidence rates and incidence rate ratios will be estimated for the occurrence of each specific endpoint regardless of a prior occurrence of any of the other study endpoints during the study period.
3. Incidence rates and incidence rate ratios will be estimated for the occurrence of all MMs and NMSCs excluding in situ carcinomas, to evaluate the role, if any, of the inclusion of noninvasive skin carcinomas.
4. Incidence rates and incidence rate ratios will be estimated for basal cell carcinoma and squamous cell carcinoma separately.
5. Incidence rates and incidence rate ratios will be estimated for cutaneous and noncutaneous lymphomas separately.
6. Incidence rates and incidence rate ratios will be estimated by strata of propensity scores to explore effect modification.
7. To evaluate protopathic bias, incidence rates and incidence rate ratios will be estimated for the first 6 months after the first exposure (ignoring lag time), and for other lag times (e.g., 12 months, 18 months, 24 months, 48 months) in addition to the predefined lag time of 6 months.
8. To explore potential surveillance bias, incidence rates of malignant melanoma and non-melanoma skin cancer will be stratified by stage of malignancy at the time of diagnosis in those data sources where information on stage is available. Data on stage of cancer at diagnosis can be useful to assess the potential role of a higher medical surveillance in the detection of cases (if lower stages are found, higher medical surveillance is likely to have occurred).
9. Incidence rates and incidence rate ratios will be estimated by severity of atopic dermatitis. In Phase I, definition of severity of atopic dermatitis was based on the utilization of health care resources. However, information was only partially available in the study data sources. In the JOELLE Extension, severity of atopic dermatitis will be defined according to the type of prescriber of the first prescription (dermatologist or nondermatologist) as a proxy for severity.

Data for the sensitivity analyses will be generated by each database research partner, and the overall analysis will be conducted by the coordinating center.

